#### 8.9 Trial assessments

Table 2 (page 46) lists all the trial assessments per visit.

#### 8.9.1 Non laboratory procedures

- Medical History: The medical history will be taken by the delegated trial team member from the participant and by referring to medical notes where possible to assess eligibility.
- Breathalyser tests will be used at each visit for the following reasons:
  - Screening & re-screening To assess eligibility
  - Visit 2 (baseline visit, 1st infusion) To assess eligibility/ensure safety of IMP administration/ensure participant is able to complete questionnaires, as well as engage with therapy/education
  - Visits 3, 5, 7 and 8 To ensure participant is able to complete questionnaires, as well as engage with therapy/education
  - Visits 4 and 6 (2nd and 3rd infusion) To ensure safety of IMP administration/ensure participant is able to complete questionnaires, as well as engage with therapy/education
  - Visits 9 and 10 To ensure participant is able to complete questionnaires
  - Once randomised, if a participant attends for any visit highly intoxicated (above 0.035 BAC

     legal driving limit) the visit may be terminated (either for the primary purpose of safety on infusion visits or of data integrity on non-infusion visits) and the participant invited to re-attend to complete the visit within the allocated visit window. If the participant fails to attend the re-arranged visit they will be withdrawn from the treatment but will continue follow-up visits.
- Vital Signs: Oral/tympanic temperature, resting pulse, pulse oximetry and blood pressure (BP) measurements will be measured at each visit phase for safety monitoring. During the infusions vital signs will be continuously monitored throughout the infusion and then at 20 minutes intervals until the participant has recovered. This monitoring will be recorded on a standard observation chart, stored as source data. The eCRF will record 3 sets of readings, one prior to the infusion, another after the infusion terminates, and then finally after the participant's recovery.

- Concomitant Medication and allergies: All prescription medication, over-the-counter medication, vitamins, and/or herbal supplements will be recorded on the concomitant medications eCRF and reviewed by a trial medic.
- Physical Examination: Height, weight and oral/tympanic temperature will be recorded.
  - At screening a physician will perform a physical examination of the cardiovascular, respiratory, GI, GU and neurological system to a level of detail that would be expected for a participant due to receive anaesthesia.
- Home assessments:
  - Participants will be required to self-breathalyse each morning using a breathalyser provided by the trial team. Breathalyser information will be recorded in a diary which will be shown to the therapist/research nurse at each visit to record readings.
  - BACtrack Skyn: participants will wear an alcohol monitoring device around their wrist during the trial which measures transdermal alcohol content in sweat. Participants will be required to download the data from their BACtrack Skyn every few days *via* BlueTooth to their iOS device.

The assessment days at which questionnaire and neurocognitive measures will be administered can be found in Table 2. Below is a list of questionnaire and neurocognitive measures and their state of validation:

Validated Interviews and Questionnaires:

- The Structured Clinical Interview for DSM-5 Disorders (SCID) is used to confirm a diagnosis of alcohol use disorder and the absence of current psychiatric diagnoses or SUDs that are listed as exclusion criteria (e.g. psychotic disorders including schizophrenia). This diagnostic schedule is widely used and lasts 20-30 minutes.
- The Clinician Alcohol withdrawal symptom checklist assesses alcohol withdrawal symptoms [63].
- The Beck Depression inventory (BDI) is a 21-item self-rated questionnaire which will be given at varying time points to measure depressive symptoms.
- The Columbia Suicide Severity Rating Scale (C-SSRS) is a 6-item interview used to assess suicidal ideation and behaviour using the "Baseline/Screening" version and will be used to verify the exclusion criteria of subjects with suicidal ideation at the screening visit.

- The Fagerstrom Test of Nicotine Dependence (FTND) is a 5-item scale to index nicotine dependence.
- The SF-36 is a short scale that measures social functioning.
- The alcohol TimeLine Follow Back (TLFB) is a drinking assessment method that obtains estimates of daily drinking and has been evaluated with clinical and nonclinical populations. Using a calendar, people provide retrospective estimates of their daily drinking over a specified time period. Several memory aids can be used to enhance recall (e.g., calendar; key dates serve as anchors for reporting drinking; standard drink conversion). The alcohol TLFB has been shown to have good psychometric characteristics with a variety of drinker groups, and can generate variables that provide a wide range of information about an individual's drinking (e.g., pattern, variability, and magnitude of drinking).
- Participants will be given access to a drink diary to use at home in between Visits 8, 9 and 10.
   Participants will be asked to record their alcohol consumption every day in between trial visits.
   Drink diaries are regularly used in alcohol research to record subjective alcohol consumption.
- Alcohol Craving Questionnaire short-form (ACQ-NOW) is a 12-item scale that assesses current alcohol craving.
- Montgomery-Asberg Depression Rating Scale (MADRS) is a clinical interview used in patients with suspected depression and rates patients on a variety of depression related scales.
- Alcohol Abstinence Self Efficacy Scale is a 20-item self-report questionnaire which evaluates a person's potential to abstain from drinking alcohol.
- Snaith-Hamilton Pleasure Scale (SHAPS) is a questionnaire used to assess the presence of anhedonia.
- Ketamine side-effect scale (KSET) is a questionnaire that assesses acute and longer-term side effects associated with ketamine treatments.
- Clinician-Administered Dissociative States Scale (CADSS) is a structured clinical interview to assess state dissociation rated by clinicians.
- SADQ- Severity of Alcohol Dependence Scale assesses current severity of alcohol dependence.
- World Health Organisation alcohol use disorders inventory categorises risk level of current drinking.
- EQ-5D-5L- assesses health-related quality of life.
- ICECAP-A assesses wellbeing and capability in adults for economic evaluation.
- Stanford Expectancy of treatment questionnaire [64] assesses patient expectancy of treatment outcome in clinical trials.

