#### 3. ASSESSMENT AND MANAGEMENT OF RISK

Excellent safety and tolerability data suggest that the risks of ketamine treatment would be low. Ketamine is currently indicated as an anaesthetic agent for diagnostic and surgical procedures. The use of ketamine for this anaesthetic purpose administers higher doses (1mg/kg to 4.5mg/kg over 60 seconds) than our proposed dose of 0.8mg/kg over 40 minutes, and even at these higher doses ketamine has a very good safety profile [56]. Ketamine is suggested to be used with caution in chronic alcohol dependence and the acutely alcohol-intoxicated patient. However, this is for anaesthetic doses and our phase II study indicated better liver function following treatment. Breathalysers will be used to exclude participants currently intoxicated with alcohol.

The Summary of Product Characteristics (SmPC) states that dose reductions should be considered in alcohol dependent patients: our trial does intend to use less than the minimum clinical dose of 1mg/kg as the SmPC indication is for use in anaesthesia. The SmPC also states that abnormal Liver Function Tests (LFTs) associated with ketamine use have been reported, particularly with extended use (>3 days) or drug abuse. Ketamine will be used at a lower dose than anaesthetic levels and will only be given in 3 isolated low doses, spaced at weekly intervals. Ketamine has a very short half-life and so will be quickly eliminated from the system [57].

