# 7.1 Inclusion criteria

- 1. 18 years old or over
- 2. Meet DSM-5 criteria for severe AUD
- 3. Abstinent from alcohol at randomisation (verified with withdrawal symptom checklist and breathalyser BAC level 0.00)
- 4. Seeking to reduce or quit alcohol long-term.
- 5. Willing and able to consent and comply with trial procedure.
- People of childbearing potential and their sexual partners must be willing to use an effective method of contraception\* (and must agree to continue for 6 weeks after the last dose of the IMP). Participants must be willing to inform the trial team if pregnancy occurs.
- 7. People of childbearing potential must have a negative pregnancy test within 28 days prior to being registered for trial treatment and on the day of first treatment.

\* Highly effective contraception is defined as one of the following: combined (estrogen and progestogen containing) hormonal contraception associated with inhibition of ovulation (oral, intravaginal, or transdermal); progestogen-only hormonal contraception associated with inhibition of ovulation (oral, injectable, or implantable); intrauterine device; intrauterine hormone-releasing system; bilateral tubal occlusion; vasectomised partner; practising true abstinence (when this is in line with the preferred and usual lifestyle of the subject). People of child-bearing potential could also be post-menopausal (no menses for 12 months without an alternative medical cause) or be surgically sterile (hysterectomy, bilateral salpingectomy, or bilateral oophorectomy).

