# 8.7 Treatment procedures (visits 2 (i.e. baseline; 14 to 28 days after screening), visit 4 (4 to 21 days after visit 2) and 6 (4 to 21 days after visit 4))

Participants will receive a weekly phone call from site staff reminding them of their next appointment date.

**Infusion:** Randomised participants will receive either 3 infusions of ketamine (0.8mg/kg made up to 50ml with saline over 40 minutes) or 3 infusions of ketamine (0.05mg/kg made up to 50ml with saline over 40 minutes), see section 9. Infusions will be administered over three weeks. The infusion will be prepared by unblinded pharmacy staff) or delegated unblinded site staff at the trial site facility. The infusion dose will be blinded to the research medic/nurse at the trial site who will administer the infusion. The total amount of ketamine hydrochloride to be delivered will be calculated on the participant's weight (0.8 or 0.05 mg/kg). Site pharmacy (or unblinded site staff) will order ketamine and dispense per participant, added to saline (0.9%) to make up to 50ml in syringes/bags for the syringe/infusion pump. Doses will be administered using a computer-controlled syringe pump if a syringe has been prepared, or a computer-controlled infusion pump if an infusion bag has been prepared. Participants will be given the option of whether they would like to listen to non-vocal instrumental music during the infusion to block out environmental noise.

**Mindfulness Based Relapse Prevention Therapy (MBRP):** A seven session manualised intervention and accompanying workbook developed with alcohol Specialist Clinical Psychologists (the supporting documents will give the details for manual and workbook). MBRP incorporates mindfulness practices alongside traditional cognitive-behavioural relapse prevention interventions [78]. The aim of these 7 sessions is to help to reduce the risk of relapse and support participants to develop an enjoyable and meaningful life without alcohol. It focuses around two broad themes, relapse prevention and promoting wellbeing, with mindfulness practice incorporated throughout the 7 sessions. Homework assignments will be used to promote incorporation of skills and strategies introduced into participants' daily lives.

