#### 9.6 Dosage schedules

Three infusions will be administered at weekly intervals, one each at visits 2, 4 and 6. Doses will be made up from a neutral glass vial/ampoule with rubber closure and aluminium flip-off cap containing ketamine hydrochloride. The total amount to be delivered will be calculated on the basis of the participant's screening visit weight.

Site pharmacy / unblinded site staff will order ketamine and dispense per participant, added to saline (0.9%) to make up to 50ml solution in syringes/bags for the syringe/infusion pump to infuse intravenously over 40 minutes. Doses will be administered using a computer-controlled syringe pump if a syringe has been prepared, or a computer-controlled infusion pump if an infusion bag has been prepared.

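### At infusions 2 and 3 the protocol permits, but does not require, sites to withhold ketamine when the breathalyser reads above 0.035

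*Protocol*

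**What the plan says.** Section 3 of the protocol gives the background: "Ketamine is suggested to be used with caution in chronic alcohol dependence and the acutely alcohol-intoxicated patient". It goes on to say that this caution concerns anaesthetic doses, and then states a mitigation: "Breathalysers will be used to exclude participants currently intoxicated with alcohol".

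For entry, inclusion criterion 3 in section 7.1 reads "Abstinent from alcohol at randomisation (verified with withdrawal symptom checklist and breathalyser BAC level 0.00". Section 7 allows no waivers. Randomisation takes place at visit 2, which is also the first infusion visit.

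Section 9.6 sets out the dosing: "Three infusions will be administered at weekly intervals, one each at visits 2, 4 and 6". The section 8.7 heading gives the windows: "visit 4 (4 to 21 days after visit 2) and 6 (4 to 21 days after visit 4".

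Section 8.9.1 lists why the breathalyser is used at each visit. For the later infusions it says "Visits 4 and 6 (2nd and 3rd infusion) To ensure safety of IMP administration", followed by fitness for questionnaires and therapy. The action rule comes at the end of that list and applies once a participant is randomised: "if a participant attends for any visit highly intoxicated (above 0.035 BAC", then "the visit may be terminated (either for the primary purpose of safety on infusion visits", or for data integrity at non-infusion visits. The participant is invited back within the visit window. Anyone who fails to attend the re-arranged visit is withdrawn from treatment but stays in follow-up.

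**The concern.** A test whose stated purpose is safe dosing should come with a reading at which the dose is not given. Section 8.9.1 supplies a figure but attaches only an option to it, and the sentence covers infusion visits expressly, so the option cannot be read as meant for questionnaire visits alone. A site that infused at visit 4 or 6 with a reading above 0.035 would not have broken this rule. Below that figure the section says nothing about whether a positive reading matters for dosing.

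At stake are participant safety and consistent practice across up to ten sites. Lapse is foreseeable: section 10.2.1 lists it among the expected events. Section 9.7 rules out dose modification, so there is no reduced dose to fall back on; the infusion is either given at the allocated dose or not given.

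**Working it through.** No figure in the plan needs reproducing. The check sets the rules side by side and then counts the infusions each one governs.

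**Rules by infusion**

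| Infusion | Visit | Reading above 0.00, up to 0.035 | Reading above 0.035 |
|---|---|---|---|
| 1 | 2 | Not eligible for randomisation (7.1) | Not eligible for randomisation (7.1) |
| 2 | 4 | No action stated (8.9.1) | Visit may be stopped (8.9.1) |
| 3 | 6 | No action stated (8.9.1) | Visit may be stopped (8.9.1) |

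**Does another section supply a binding alcohol stop at visits 4 and 6?**

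- Section 9.11 (fasting): six hours without food or drink other than water, and no water for the last two. An infusion is delayed if this is not met. That is mandatory, but it depends on what the participant reports and sets no alcohol level. Alcohol remaining from drinking before the six hours is not covered.
- Section 9.10 (concomitant medication): central nervous system depressants are barred on treatment days. Alcohol is not named and no reading is given.
- Section 7.2, criteria 13 and 14 (label warnings; unfavourable risk against benefit): these are entry criteria. Section 8.12 lets an investigator discontinue someone who becomes ineligible, but this too is optional.
- Table 4 (urine alcohol test at every visit) and the home breathalyser diary in 8.9.1: these provide information, with no dosing rule attached.

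None of them sets a binding alcohol limit for infusion 2 or 3.

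**How the protocol words other stops.** A missed fasting window leads to a delayed infusion (9.11). A positive urine screen for ketamine after randomisation leads to withdrawal from treatment (8.12). Both are stated as what happens, not as what may happen, so the softer verb for alcohol stands out.

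**How many infusions the discretionary rule governs**

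- Planned infusions: 280 × 3 = 840.
- At visits 4 and 6: 280 × 2 = 560.
- Share: 560 / 840 = 66.7%.
- Time since the 0.00 check at visit 2: infusion 2 at 4 to 21 days; infusion 3 at 4 + 4 = 8 to 21 + 21 = 42 days.

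The 560 assumes that every participant receives every infusion, so it is a ceiling. It covers both dose groups.

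**The case against.** The strongest reply is that nothing here conflicts. *Exclude* in section 3 can mean exclusion from the trial: section 3.1 speaks of declining entry to people with contraindications, and uses *excluded* for other substance use in the same sense. On that reading criterion 3 delivers the commitment in full. The 0.00 level belongs to a criterion about abstinence at randomisation, verified together with a withdrawal checklist; it is not presented as a dosing limit. The only number the protocol ties to intoxication is 0.035. The ketamine caution is qualified as applying to anaesthetic doses, which are higher than the 0.8 or 0.05 mg/kg given here. Fasting, urine testing, continuous monitoring during the infusion and the judgement of the clinician present all make it less likely that an intoxicated participant is dosed.

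Most of this stands. A reader might infer that section 3 and section 8.9.1 cannot both be true, or that any reading that would have blocked infusion 1 must also block infusions 2 and 3. The documents do not support either inference, for the reasons just given.

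The reply does not reach section 8.9.1 itself. That section gives safe administration as a purpose of the test at visits 4 and 6, labels readings above 0.035 as highly intoxicated, names safety as the ground for stopping an infusion visit, and then makes stopping optional. The narrow reading of section 3 does not explain that choice, and the other safeguards reduce the risk without setting a limit.

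**Conclusion.** The point holds as a loose safety rule, not as a contradiction. As written, infusions 2 and 3 may be given to a participant above 0.035, and section 8.9.1 sets no limit for giving the infusion at lower positive readings. The rule covers up to 560 of 840 planned infusions. How many would involve a positive reading is unknown, since the protocol gives no rate, and none is assumed here.

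The conclusion rests on reading *may* as discretionary and on no other section of the protocol setting an alcohol stop. A site work instruction might do so, but none is shown. Nothing is claimed about a rate of harm, an effect on the primary outcome, or the unit or legal meaning of 0.035. This is a cheap improvement worth making; it does not put the trial's conclusions in doubt.

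**What to change.** In section 8.9.1, separate infusion visits from the rest. For visits 4 and 6, state that when the reading is above 0.035 the IMP will not be given and the visit will be re-arranged within its window. Keep the discretionary wording for non-infusion visits.

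Whether to lower the infusion limit to 0.00, the level already required for randomisation, is for the sponsor to decide. It would be simpler for sites, but it would re-arrange more visits for a benefit the documents do not quantify.

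The cost is a sentence or two in 8.9.1, a protocol amendment and a note to sites. A few more infusions will be re-arranged. Some participants may be withdrawn from treatment, because 8.9.1 does this when the re-arranged visit is missed. Their follow-up continues, so they remain available to the treatment policy analysis in section 11.3.3. They would leave the per protocol set, which requires all three infusions. No analysis needs to change.

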# REDACTED Version 8.0, 18/JUN/2024; IRAS ID: 1008179

Page 62 of 105

- BANG blinding index assesses the success of blinding in clinical trials [65].
- Clinical Global Impression: provides a brief, stand-alone assessment of the clinician's view of the patient's global functioning prior to and after initiating a trial medication [66]. This will be assessed by a psychiatrist either in person or remotely at trial visits.
- Hood Mysticism Scale is a questionnaire aimed at assessing mystical experiences.
- 3 Things Task is a standardised task to activate context-relevant aspects of the self-concept [67] which allows for the assessment of the self-concept with natural language processing tools such as ASIA [11].
- Acceptance/Avoidance-Promoting Experiences Questionnaire (APEQ) assesses psychological flexibility.
- The Beck Anxiety Inventory (BAI) assesses severity of anxiety using a 21-item questionnaire.
- The Childhood Trauma Questionnaire (CTQ) is a retrospective screening tool for childhood maltreatment in adults.
- The Readiness to Change scale is a 12-item questionnaire looking at motivational stages of change and has been used previously in high-risk alcohol consumers [x].

Questionnaires that are not validated:

- The Pre-Screening questionnaire has been developed to assess suitability for inclusion into the trial.
- A semi-structured interview detailing the participant's alcohol and drug use history will also be used.

#### 8.9.2 Laboratory procedures

In order to assist the identification of pathology and confirm physical health and eligibility for inclusion in the trial, various blood tests and urine tests will be performed. A trial specific laboratory manual will be provided to sites. Tables 3 and 4 below respectively outline which blood tests and urine tests should be completed as part of the screening visit as well as at each subsequent visit for randomised participants.

All laboratory results will be reviewed and reports signed by the delegated trial team medic, and the site team will record in the eCRF whether they were deemed normal, abnormal but not clinically significant or abnormal AND clinically significant. In the latter case the eligibility of participants will be reviewed. Table 3 outlines which blood tests should be carried out at each visit.

REDACTED Version 8.0, 18/JUN/2024; IRAS ID: 1008179 MORE-KARE protocol Page 63 of 105

					Visit						
		1 (Screening)	2 (Baseline)	3	4 (Infusion)	5	6 (Infusion)	7	8	9 (3m	10 (6m
										, FU)	FU)
	Urea	Х									
	Sodium	Х									
	Potassium	Х									
	Glucose	Х									
	Calcium	Х									
Biochemistry	Thyroid stimulating hormone	x			5						
	Haemoglobin	Х									
	White cell count	x			-						
ology	Platelets	Х	Х		Х		Х		Х	Х	Х
Haematology	Mean red cell volume	x									
	Bilirubin	Х	Х		Х		Х		Х	Х	Х
	ALT	Х	Х		Х		Х		Х	Х	Х
	Albumin	Х	Х		Х		Х		Х	Х	Х
tion	Gamma-GT	Х	Х		Х		Х		Х	Х	Х
Liver function	AST	Х	Х		Х		Х		Х	Х	Х
Liver	ALP	Х	Х		Х		Х		Х	Х	Х

#### Table 3: Blood tests to be carried out at each trial visit.

Ketamine Co Lo Lo Lo Lo Lo Lo Lo Lo Lo Lo Lo Lo Lo	X*	X*	X*	x	х	х
--	----	----	----	---	---	---

\* On infusion days (visits 2, 4 and 6) blood samples will be taken pre- and post-infusion to assess changes in ketamine levels. Blood samples taken after the infusion will be collected after the participant has recovered from the infusion (2 hours after the infusion finishes). Pre-infusion samples to be taken from the cannula before the infusion. Post-infusion samples to be taken via venepuncture from a different site.

All biochemistry, haematology and liver function tests will be processed at a local Trust laboratory as per Trust policy for processing and analysis. Results should be made available for review by the trial medic and documented in the blood sample eCRF. All exploratory samples (i.e. for ketamine analysis) should be spun and stored in a -80°C freezer at a local laboratory before being periodically couriered to a HTA licensed central laboratory for analysis, details will be specified in the laboratory manual.

The Table 4 below outlines which urine tests will be performed at site using kits provided by Exeter CTU with results recorded in the eCRFs for all trial visits.

	Visit												
	1	2	3	4	5	6	7	8	9	10			
	(Screening)	(Baseline)		(Infusion)		(Infusion)			(3m	(6m			
									FU)	FU)			
Pregnancy test	X	Х		Х		Х							
Methamphetamine	Х	Х	Х	Х	Х	Х	Х	Х	Х	Х			
Cocaine	Х	Х	Х	Х	Х	Х	Х	Х	Х	Х			
THC	Х	Х	Х	Х	Х	Х	Х	Х	Х	Х			
Benzodiazepines	Х	Х	Х	Х	Х	Х	Х	Х	Х	Х			
Ketamine	Х	Х		Х		Х		Х	Х	Х			

Table / (	Jutlings	which u	ring tasts	are to	he	norformod	at each visit.
	Julines	which u	ine testa		NC	periormeu	

REDACTED Version 8.0, 18/JUN/2024; IRAS ID: 1008179

Page 65 of 105

Amphetamines	Х	Х	X	Х	Х	Х	Х	Х	Х	Х
Morphine	Х	Х	Х	Х	Х	Х	Х	Х	Х	Х
Methadone	X	Х	Х	Х	Х	Х	Х	Х	Х	Х
Alcohol	X	Х	Х	Х	Х	Х	Х	Х	Х	Х

People being actively treated for a current co-morbid substance use disorder (past 12 months), see section 7 will be excluded from the trial. Cannabis and benzodiazepine use are being monitored throughout the trial. However, cannabis consumption leads to THC remaining in the urine for approximately 28 days. Therefore, occasional cannabis use may result in a positive THC result. However occasional cannabis use is not grounds for exclusion as long as participants do not have a cannabis use disorder. Benzodiazepines are used in community detox and for sleep problems. Benzodiazepine use has a relatively long detection window, up to 7 days for long acting. Therefore, benzodiazepine use in detox may lead to a positive urine test. However, use of benzodiazepines in detox is not grounds for exclusion as long as participants do not have a benzodiazepine use disorder.

All urine samples will be analysed on the day of collection and will be disposed of after processing according to local processes for urine disposal. Results should be recorded in the urine sample eCRF.

